4.1.1 Baseline

Baseline is defined as the last available measure prior to vaccination with ABNCoV2 (first vaccination for Group 1, single boost vaccination for Groups 2 and 3). Baseline values may come from the screening, first vaccination visit, or an unscheduled visit prior to the first

vaccination visit. If multiple pre-vaccination values are available, the one closest in time to the ABNCoV2 vaccination will be used as the baseline value. In the event that no time is collected for a value measured on the date of first vaccination, measurements required to be collected prior to vaccination per the clinical trial protocol will still be considered eligible for inclusion as baseline measurements.

Subjects missing baseline values will not be included in change/shift from baseline or ratio to baseline analyses, including the Groups 2 and 3 analyses of the primary estimand.

4.1.2 Analysis Sets

In general, the Immunogenicity Analysis Set will be used for analyses of immunogenicity. The Safety Analysis Set will be used for sensitivity immunogenicity analyses, secondary endpoint analyses, as well as all safety, demographics, and disposition analyses. For further details, see Section 3.

4.1.3 Study Periods and Windowing

The following study periods are defined for this trial:

Screening Period: The period from the subject's signing of informed consent to the trial through the date and time of first vaccination. AEs starting during this period are considered Baseline Signs and Symptoms.

Active Trial Period: The period from the first vaccination up to and including week 4 (28-35 days) after receiving their vaccination. A visit at the end of the Active Trial Period is scheduled per protocol. In the event of early withdrawal of a subject from the trial during the Active Trial Period, the EAP visit may occur prior to the 28-35 days post-last vaccination window. For the purpose of safety analyses, any safety information collected within 35 days of their vaccination received will be included in summaries of the Active Trial Period.

FU Period: The period from the EAP visit through the final follow up visit. Subjects have 3 FU visits at 4, 9 and 22 weeks after the scheduled EAP visit (Weeks 8, 13 and 26). Subjects may withdraw from treatment early but continue into the FU Period.

For assigning prior and concomitant medications, those ending prior to the first vaccination are considered prior medications. All other medications are considered concomitant medications.

For AEs and medications with partial or missing start and/or stop dates, the “worst case” should be applied to be conservative. Therefore, the following rules will apply:

AEs

- If start date is partial and any portion (i.e., year or month and year) would confirm the AE was prior to first vaccination, the AE will be considered a Baseline Sign or Symptom.
- If the start date is completely missing and the end date, or any portion of a partial end date, confirms the AE ended prior to first vaccination, the AE will be considered a Baseline Sign or Symptom.
- Otherwise, the AE will be considered as belonging to the Active Trial Period.

Medications

- If the end date is partial, and any portion confirms the medication was ended prior to first vaccination, the medication will be considered a Prior Medication.
- Otherwise, the medication will be considered a Concomitant Medication.

Per protocol, all visits are to occur within the specified window in the Trial Schedules ([Appendix 2](#) and [Appendix 3](#)). For the purpose of the primary estimand, rules for inclusion into the Immunogenicity Analysis Set will ensure immunogenicity samples taken too far out of window will not be included for analysis. For sensitivity analyses, immunogenicity samples taken out of window will be handled as described in Section [4.2.3.1](#).

In general, safety analyses will be performed for the Active Trial Period, accounting for any observations between the first vaccination and the EAP visit, inclusive of the EAP visit and any unscheduled visits during this period. In the event of early discontinuation from the Active Trial Period (i.e., EAP occurs prior to one month post last vaccination), safety results through 35 days (upper limit of the EAP visit window) post-last vaccination will be analyzed along with the Active Trial Period summaries. For Group 1, safety summaries will be performed by vaccination as well as for the overall Active Trial Period. Nominal visits will be used for the by-visit summaries, with the worst/highest toxicity grade value presented for the visit in the case of multiple reported observations.

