4.5.2.2 Unsolicited Adverse Events

All intercurrent diseases reported when the investigator actively inquires the subject will be documented as unsolicited adverse events. Unsolicited AEs will be assessed and documented from ICF signature through EAP, and if ongoing at that time followed until resolution or until the subject's last trial visit, at the latest. SAEs and AESIs will be collected through the end of the trial, including during the FU period, and followed-up until resolution or achievement of stable clinical conditions.

Relationship of the trial vaccine to the AE is assessed by the investigator using the categories "none," "unlikely," "possible," "probable," and "definite." An AE assessed as possibly, probably, or definitely related will be counted as a related AE for the purpose of reporting. AEs categorized as none or unlikely for causality will not be considered related to trial vaccination. AEs missing a relationship will not have a causality imputed.

Unsolicited AEs are graded based on the *Toxicity Grading Scale for Healthy Adult and Adolescent Volunteers Enrolled in Preventive Vaccine Clinical Trials* ([FDA, 2007](#)). The maximum toxicity grade over the duration of the AE will be reported in the case report form. If a subject has multiple AEs within the same PT, the highest toxicity grade will be used for subject-level summaries. Grading will be based on the descriptions listed in [Table 5](#).

Table 5 Adverse Event Grading

Grade	Definition
Grade 1	An AE which is easily tolerated by the subject, causing minimal discomfort and not interfering with daily activities.
Grade 2	An AE which is sufficiently discomforting to interfere with daily activities, but does not require medical intervention (non-narcotic pain reliever or other nonprescription medication are not considered "medical intervention" for this purpose).
Grade 3	An AE which prevents daily activities and which requires medical intervention (non-narcotic pain reliever or other nonprescription medication are not considered "medical intervention" for this purpose)
Grade 4	Life-threatening, or disabling.

Analysis

The secondary estimand analyses for SAEs, AESIs, and related \geq Grade 3 AEs within 8 days after vaccination are described in [Section 4.3](#).

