In general, AEs will be summarized by SOC, PT, and group for the Safety Analysis Set in the Active Trial Period. AEs occurring after the Active Trial Period during the FU period will be included in the AE listings. AEs occurring between ICF signature and first vaccination will be

considered Baseline Signs and Symptoms and will be reported similarly to medical history events.

For Group 1, summaries will also be included by period for Vaccination Period 1, Vaccination Period 2, and the overall Active Trial Period. For the overall Active Trial Period, event counts will include events from both vaccination periods in the case a subject experiences the same event multiple times.

Groups 2 and 3 will be summarized for the Active Trial Period, separately from Group 1.

An overall summary of solicited and unsolicited AEs including subject counts, event counts, percentages (of subjects only) will be created for the following event categories:

Solicited and Unsolicited AEs

- All AEs
- SAEs
- AEs Leading to Withdrawal
- Fatal AEs

Solicited AEs

- Local AEs
 - \geq Grade 3
 - Leading to Deferral or Discontinuation of Vaccine
 - SAEs
- General AEs
 - \geq Grade 3
 - Related
 - Related \geq Grade 3
 - Leading to Deferral or Discontinuation of Vaccine
 - SAEs

Unsolicited AEs

- All AEs
 - Related
 - \geq Grade 3
 - Related \geq Grade 3

- Leading to Withdrawal
- SAEs
 - Within 8 Days After Vaccination
 - Within 29 Days after Vaccination*
 - Related SAEs
 - Fatal
- AESIs
 - Within 8 Days After Vaccination
 - Within 29 Days after Vaccination*
 - Related AESIs
- Related AEs \geq Grade 3
 - Within 8 Days After Vaccination
 - Within 29 Days after Vaccination*

*Within 29 days summaries includes through the day prior to second vaccination for Group 1 Vaccination Period 1, or from the last/single booster vaccination through the end of the Active Trial Period for all groups. The window for the end of the Active Trial Period visit is 28-35 days post last/single booster vaccination.

Summary tables for unsolicited AEs by SOC and PT will be presented including subject and event counts and percentages (of subjects only) for the Active Trial Period:

- AEs
- Related AEs
- AEs \geq Grade 3
- Related AEs \geq Grade 3
 - Related AEs \geq Grade 3 Occurring within 8 Days of any Vaccination
 - Related AEs \geq Grade 3 Occurring within 29 Days of any Vaccination*
- Non-serious AEs in $> 5\%$ of Subjects
- SAEs
- Related SAEs
 - Related SAEs Occurring within 8 Days of any Vaccination

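### The SAP's partial-date rule for adverse events has no follow-up outcome, so an SAE or AESI whose known month or year proves late onset is assigned to the Active Trial Period

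*SAP*

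**What the plan says.** SAP 4.1.3 sets out a Screening Period and two post-vaccination periods. The Active Trial Period is "The period from the first vaccination up to and including week 4 (28-35 days) after receiving their vaccination". The FU Period is "The period from the EAP visit through the final follow up visit". The last paragraph of the section adds that, if the EAP visit comes early, safety results up to day 35 after the last vaccination still count with the active period.

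For incomplete dates the section begins: "For AEs and medications with partial or missing start and/or stop dates, the “worst case” should be applied to be conservative". Three AE bullets follow.

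- Partial start date: "If start date is partial and any portion (i.e., year or month and year) would confirm the AE was prior to first vaccination", the event is a Baseline Sign or Symptom.
- Start date wholly missing: if the end date, or a known part of it, "confirms the AE ended prior to first vaccination, the AE will be considered a Baseline Sign or Symptom".
- Everything else: "Otherwise, the AE will be considered as belonging to the Active Trial Period".

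SAP 4.5.2.2 extends collection well beyond the active period: "SAEs and AESIs will be collected through the end of the trial, including during the FU period". It also says where later events are reported: "AEs occurring after the Active Trial Period during the FU period will be included in the AE listings". SAP 4.5.3.5 takes the same line for physical examination findings, which after the active period appear in AE listings and nowhere else.

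**The concern.** The section names three periods, but the incomplete-date bullets can reach only two of them. Both tests ask whether the event came before the first vaccination. None asks whether it came after the active period. A follow-up SAE or AESI recorded with month and year only is not before vaccination, so it drops to the default and becomes an active-period event, even where the recorded month excludes that.

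A worst-case rule is meant to settle doubt about timing. Here the known part of the date leaves no doubt, so the default overrides information the sponsor holds. The SAP does use the known part to exclude the active period on the early side, but not on the late side.

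What is at stake is a post-vaccination SAE/AESI table that could carry an event known not to have occurred in that window. The footnotes in SAP 4.5.2.2 run the 29-day rows to the end of the Active Trial Period, so a defaulted event could appear there too. If related, it could also enter the supplementary 29-day analysis in SAP 4.3.1.4.

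**Working it through.** The plan gives no figure to reproduce on this point. The check applies the rule as written and then sizes one misplaced event.

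**Step 1. Apply the rule to an example.** Assume a Group 2 subject vaccinated in November 2021 with an SAE start recorded as June 2022 (both dates are illustrative).

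- Latest possible end of the active period: 30 November 2021 + 35 days = 4 January 2022.
- Earliest possible onset: 1 June 2022, so onset is certainly in follow-up.
- Bullet 1: June 2022 is not before November 2021, so it does not apply.
- Bullet 2: the start date is not wholly missing, so it does not apply.
- Bullet 3: the event is assigned to the Active Trial Period.
- SAP 4.5.2.2 would place the same event in the listings as an FU-period event.

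The result does not depend on the dates chosen. No bullet leads to the FU Period, so every follow-up onset with a month-and-year start date is classed as active-period.

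**Step 2. How often would the known part settle the matter?** Inputs from the visit schedules (SAP Appendices 2 and 3):

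- Groups 2 and 3: active period to day 35, last visit by day 736, so 736 − 35 = 701 follow-up days.
- Group 1: active period to day 35 + 35 = 70 after V1, last visit by day 35 + 105 = 140, so 70 follow-up days.

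I took 365 consecutive vaccination dates from 1 August 2021 (an assumption) and counted the follow-up days whose month and year, or year alone, fall after the end of the active period.

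| Known part | Groups 2/3, mean (range) | Group 1, mean (range) |
|---|---|---|
| Month and year | 97.9% (95.7 to 100%) | 79.0% (57.1 to 100%) |
| Year only | 74.0% (48.1 to 100%) | 9.7% (0 to 100%) |

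These are shares of calendar days, not of events. They show how far a third test would sort partial dates; the rest stay ambiguous and keep the default.

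**Step 3. Size of one misplaced related event.** The Clopper-Pearson method is planned for related SAEs/AESIs (SAP 4.3.1.2, with the analysis repeated at 29 days in 4.3.1.4). Group sizes are about 90 and about 30 (SAP section 6). For x events in n subjects, the lower limit is the 0.025 quantile of Beta(x, n − x + 1) and the upper limit is the 0.975 quantile of Beta(x + 1, n − x).

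- 0/90: upper limit 1 − 0.025^(1/90) = 4.0%.
- 1/90 = 1.1%: lower limit 1 − 0.975^(1/90) = 0.03%, upper limit 6.0%.
- 0/30: upper limit 1 − 0.025^(1/30) = 11.6%.
- 1/30 = 3.3%: lower limit 1 − 0.975^(1/30) = 0.08%, upper limit 17.2%.

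**The case against.** The strongest reply is that the gap seldom bites, and much of that stands.

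- **Timing of reporting.** SAP 4.6 reports Groups 2 and 3 active-period safety first, on data cleaned through that period, and adds follow-up results later without re-analysis. A reader might infer that SAEs a year after the dose will routinely enter the Groups 2/3 tables. The documents do not support that. What remains is Group 1 (reported only at the final analysis), subjects already in follow-up at the primary cut, and any re-run of the active-period tables.
- **Completeness of dates.** Only SAEs and AESIs are collected in follow-up. Protocol 8.20 requires entry within 24 hours of awareness, with onset date in the minimum content. Partial dates remain possible, but no rate is given, and nothing shows that late events are especially prone to them.
- **Planned time.** Follow-up makes up most of the planned observation time in Groups 2 and 3. A reader might take that as the share of events at risk, but it is planned time only, and subjects who receive an approved booster leave follow-up (protocol 8.9).
- **Stop dates.** Because the lead-in mentions stop dates, a reader might infer that an ongoing follow-up SAE with a complete start date also falls to the default. That is strained. The lead-in is shared with the medication rules, and the second AE bullet needs end dates. The same reading would move a screening AE with a complete pre-vaccination start date into the active period, against the Screening Period definition.
- **Direction of error.** The default over-counts rather than hides events, and the AE listings still show them individually.

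None of this supplies the missing branch. The statements in SAP 4.5.2.2 and 4.5.3.5 show the intent, but the bullets contradict it and nothing overrides them.

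**Conclusion.** The rule is wrong as written for one class of event: a follow-up SAE or AESI with a partial start date whose known part excludes the Active Trial Period. It gives that event a classification that the rest of the SAP contradicts.

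The reach is narrow, and few events are likely to be affected. The interval shifts assume that the event is assessed as related, that no other such event exists in the group, and that enrolment meets plan. An unrelated SAE or AESI would change only counts and percentages. Entry into the 29-day rows is possible rather than certain, because the bullets assign a period and impute no onset date.

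A reader might infer a general distortion of the safety result. The documents do not show one. The primary endpoint is untouched, and no effect on the 8-day secondary estimand is shown, since the default does not place an event within 8 days of a dose. The case for acting is that related SAEs/AESIs may be so few that one misplaced event is the whole numerator, and that the correction costs almost nothing.

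**What to change.** In SAP 4.1.3, insert one AE bullet before the default. If the known part of a partial start date confirms onset after the end of the Active Trial Period, assign the event to the FU Period. In programming terms, the earliest calendar date compatible with the known part must be later than that end. Define the end as the section already does: the EAP visit, or day 35 after the last vaccination if the EAP visit is early.

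Reword the default so that it applies only when the known part is compatible with the Active Trial Period. A wholly missing start date that fails the second bullet stays with the worst case.

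Add to the AE bullets that events with a complete start date follow the period definitions. Leave the shared lead-in and the medication rules unchanged; the medication rules test end dates and would be disturbed by a restriction to start dates.

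The cost is two or three sentences in the SAP and one condition in the derivation program. No data collection changes.

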4.2 Primary Estimand Analysis

4.2.1 Definition of Endpoint

SARS-CoV-2 neutralizing antibody titers (Wuhan strain, presented in WHO standardized units of IU/mL) at 2 weeks after the last vaccination, i.e., after the second vaccination in initially seronegative subjects (Group 1) and after the single boost vaccination in initially seropositive subjects (Groups 2 and 3), for subjects in the Immunogenicity Analysis Set (Section [4.1.2](#)). For Group 1, this will be the neutralizing antibody titer collected at Week 6, and for Groups 2 and 3 it will be the neutralizing antibody titer collected at Week 2.

Serum samples will be collected from subjects as outlined in the trial procedure schedule [Appendix 2](#) and [Appendix 3](#). Immunogenicity testing will be performed at [REDACTED] and at contracted laboratories if needed. [REDACTED]

Neutralizing antibody titers to SARS-CoV-2 are assumed to be log-normally distributed. Values will be transformed to the \log_{10} scale for the purpose of analysis. Imputation of values based on limits of detection and quantitation are described in [Section 4.1](#). Once analyses are performed, estimates will be back transformed to the original scale for reporting.

The intercurrent event that may have an impact on the primary estimand is COVID-19 infection prior to the Week 6 or Week 2 neutralizing antibody titer collection, respectively, for all groups. As subjects who come in contact with the virus can have significant interference with the SARS-CoV-2 neutralizing antibody levels, these subjects will be excluded from the primary analysis. This is equivalent to the “while on treatment” strategy. Reasons for exclusion from the primary estimand analysis will be summarized separately for full accounting of the study population.

The second intercurrent event of discontinuing the study prior to collection of the neutralizing antibody titer endpoint at Week 6 or Week 2, respectively, for each group is not expected to have an impact on SARS-CoV-2 neutralizing antibody levels. Therefore, the “treatment policy” strategy will be used in these cases.

As the primary estimand is specifically defined for subjects who meet the criteria to be in the Immunogenicity Analysis Set, subjects who have protocol deviations that would substantially affect the neutralizing antibody titer levels at the respective primary analysis timepoints are not included in the analysis. These subjects will be summarized in the disposition displays as being excluded from the Immunogenicity Analysis Set, as well as summarized in a table as to which deviations were observed that may have had a substantial effect on their primary endpoint value.

4.2.2 Main Analytical Approach

The estimate of the primary estimand will be created using the Immunogenicity Analysis Set, which will include only subjects who have no protocol deviations that will substantially affect the immunogenicity outcomes. Due to this, missing values for the primary estimand analysis are unexpected. Subjects who have a value for the primary time point but developed COVID-19 symptoms prior to 2 weeks after the last vaccination, and had a positive PCR result for SARS-CoV-2 infection prior to the 2 weeks after the last vaccination time point, will be excluded from the analysis due to the interference the infection will have on the resulting neutralizing antibody results.

The geometric mean of SARS-CoV-2 neutralizing antibody titers (Group 1), and fold increases (Groups 2 and 3) 2 weeks after the last vaccination, will be summarized along with their 95% CIs. No statistical hypothesis testing will be performed for this single arm trial.

Geometric mean titers (GMTs) will be obtained by computing the arithmetic means and the corresponding 95% CIs on the \log_{10} scale, and then exponentiating the \log_{10} means and confidence limits to return the results to the original scale.

Fold increases for Groups 2 and 3 will be calculated as the ratio of the SARS-CoV-2 neutralizing antibody titer at 2 weeks post-last vaccination to the baseline neutralizing antibody titer (i.e., last measurement prior to vaccination). Geometric mean fold increases (GMFIs) will be calculated in the same manner as GMTs.

4.2.3 Sensitivity Analyses

The reason for exclusion from the primary estimand analysis will be included with the sensitivity analysis for a full account of the study population. Reasons may include, but are not limited to:

- Development of COVID-19 symptoms and having a positive PCR result for SARS-CoV-2 infection prior to 2 weeks after the last vaccination
- A protocol deviation substantially affecting the immunogenicity outcome (i.e., exclusion from the Immunogenicity Analysis Set)

4.2.3.1 Sensitivity using the Safety Analysis Set

The analytical approach used for the primary estimand will be repeated using the Safety Analysis Set including any available post-last vaccination value for the primary time point (2 weeks post-last vaccination) regardless of window, and without respect to protocol deviations that may substantially affect immunogenicity outcomes. If multiple post-last vaccination neutralizing titer values are available, the value closest to the target day (2 weeks post last vaccination, i.e., Week 6 for Group 1 and Week 2 for Group 2 and Group 3) will be used for the sensitivity analysis. If two values are equidistant from the target day, the later value will be used. No pre-vaccination titer values will be analyzed as post vaccination titer results.

